# 6.3 Duration of Therapy

In the absence of treatment delays due to adverse events, treatment may continue indefinitely until one of the following criteria applies:

- Disease progression per RECIST version 1.
- The investigator considers it, for safety reasons, to be in the best interest of the patient.
- Unacceptable adverse event(s) related to treatment, defined as a grade 3 or 4 toxicity (per CTCAE v 4.03) that fails to recover to < Grade 2 in the absence of treatment within 4 weeks
- General or specific changes in the patient's condition render the patient unacceptable for further treatment in the judgment of the investigator
- Patient decision to withdraw from treatment (partial consent) or from the study (full consent)
- Pregnancy during the course of the study for a child-bearing participant

The date and reason for discontinuation must be documented. Every effort should be made to complete the appropriate assessments.

If in the opinion of the investigator, the patient demonstrates disease progression by RECIST, but the patient is demonstrating obvious clinical benefit to sunitinib therapy, the investigator may choose to continue patient on study. At the time that clinical benefit from study drug is no longer apparent, investigator will take patient off study and off study drug.

# 6.4 Duration of Follow Up

Patients will be followed for toxicity for 30 days after treatment has been discontinued or until death, whichever occurs first.

Serious adverse events that are still ongoing at the end of the study period will necessitate follow-up to determine the final outcome. Any serious adverse event that occurs after the study period and is considered to be possibly related to the study treatment or study participation will be recorded and reported immediately.

#### 7.0 DOSING DELAYS / DOSE MODIFICATIONS

#### **Table 3: Dose/Schedule Levels**

Table 3a defines treatment levels of sunitinib with dose and schedule specifications. The starting dose for all patients will be 50 mg on a 2/1 schedule. Dosing schedule may be changed to 50 mg 1 week on followed by 3 days off alternating with 1 week on and 4 days off and repeated for a 6-week cycle at outlined in table 3a for toxicities described in table 3b. Patient requiring further reduction in treatment level will be dose reduced to 37.5 mg on a 2/1 schedule, and so on per table 3a. Intra-patient re-escalation back to the previous treatment level is permitted in the absence of grade  $\geq 3$  hematologic or grade  $\geq 2$  non-hematologic treatment-related toxicity in the previous cycle. Table 3b outlines indications for withholding treatment and for reductions in treatment levels.

Treatment Level	Sunitinib dose	Schedule
Level 0 (starting dose)	50 mg	2 weeks on/ 1 week off
Level -1	50 mg	1 week on/ 3 days off alternating with 1 week on/4 days off
Level -2	37.5 mg	2 weeks on/ 1 week off
Level -3	37.5 mg	1 week on/3 days off alternating with 1 week on/4 days off
Level -4	25 mg	2 weeks on/ 1 week off
Level -5	25 mg	1 week on/3 days off alternating with 1 week on/4 days off

Table 3a: Treatment levels of sunitinib with dose and schedule specifications

Table 3b: Indications for withholding treatment and reductions in treatment levels

Grade	Туре	Management/Next Dose for Sunitinib
≤ Grade 1 +	Any except vascular +	No change in treatment level
	Hematologic	Continue at same treatment level
Grade 2	Cardiac	Continue at same treatment level except in the event of:  -Decrease of LVEF by an absolute value of 20% and to below the lower limit of normal -Non-urgent ventricular paroxysmal dysrhythmia requiring intervention.  In these cases: withhold dose until toxicity is grade ≤1, then reduce the treatment by 1 level and resume treatment. If the patient was on level 0, then need to
-	N. 1' 1	resume at level -2
	Non-cardiac and non- hematologic	Continue at same dose level
	Hematologic***	Withhold dose until ANC>1,000 and Platelets > 50,000, then resume treatment at the same level or reduce by 1 level at the discretion of the investigator.
Grade 3	Cardiac	Withhold dose until toxicity is grade ≤1 or has returned to baseline, then resume treatment at the same level or reduce the dose by 1 level at the discretion of the investigator.**
	Non-cardiac and non- hematologic*	Withhold dose until toxicity is grade $\leq 1$ or has returned to baseline, then resume treatment at the same level or reduce by 1 level at the discretion of the investigator.
	Hematologic***	Withhold dose until toxicity is grade ≤1 or has returned to baseline, then reduce by 1 level and resume treatment**.
Grade	Cardiac	Remove from protocol.
4	Non-cardiac and non- hematologic	Withhold dose until toxicity is grade ≤1 or has returned to baseline, then reduce by 1 level and resume treatment, or discontinue at the discretion of the investigator.

<sup>+Except vascular- for all vascular toxicities, including grade 1, drug must be held and appropriate treatment initiated. Sunitinib may be restarted at the discretion of the treating MD.

All intra-patient dose reductions are relative to the lowest dose level of the current cycle. If the current treatment level is -5 and the toxicity guidelines above indicate a further treatment/dose reduction is necessary, treatment should be discontinued. Patients are to be removed from study if toxicity does not resolve to grade 1 or less within

\* Patients with grade 3 asymptomatic biochemistry laboratory abnormalities may continue treatment at the same dose level without interruption at the discretion of the investigator.

\*\* Hypertension may be managed appropriately with anti-hypertensives, and the patient may continue sunitinib provided the blood pressure is controlled to < 160/90 mmHg within 4 weeks. Patients who are unable to have blood pressure controlled to < 160/90 mmHg within 4 weeks should be removed from the study. **Patients with congestive heart failure must be removed from study.** 

\*\*\*Patients who develop grade 3 or 4 lymphopenia may continue study treatment without interruption.

4 weeks off study drug.

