The primary DLT in the phase 1 studies appeared to be fatigue/asthenia, which generally occurred 10 to 15 days after start of therapy, and was readily reversible upon discontinuation of sunitinib malate treatment. Fatigue appeared to increase in frequency with an increase in drug exposure. DLT experienced during the first cycle of therapy was observed more frequently in subjects on Schedule 4/2 than in subjects on Schedule 2/2. Overall, the most frequent adverse events associated with sunitinib malate treatment of greatest severity have been constitutional (fatigue/asthenia), gastrointestinal (nausea, vomiting, diarrhea), and hematologic (neutropenia, thrombocytopenia). The degree of adverse event severity appears to correlate with higher drug exposure and/or lower subject performance status. A similar pattern was observed for subjects with previous chemotherapy in comparison to chemotherapy-naïve subjects.

In studies evaluating starting doses that ranged from 75 to 100 mg daily, cardiac hypokinesis and clinical signs of congestive heart failure were reported in 4 of 62 advanced acute myeloid leukemia subjects; however, the causal relationship to sunitinib malate was confounded by disease morbidities and prior anthracycline exposure. At the 50-mg dose level, asymptomatic

decreases in cardiac ejection fraction were observed in <5% of solid tumor subjects, either with or without a prior history of cardiovascular disease or anthracycline exposure. Decrease in LVEF by MUGA is reversible and does not appear to have cumulative effect with repeat drug exposure. A review of cardiac and other safety data from clinical and preclinical studies is provided in the Investigator Brochure.

The maximum tolerated dose has been defined as 50 mg in phase 1 clinical studies in subjects with advanced solid tumors, subjects with AML, and subjects with imatinib mesylate-resistant GIST. Subjects receiving this dose of sunitinib malate achieved target plasma concentrations of sunitinib malate plus SU012662 in the range of 50 to 100 ng/mL.

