#### 16.5 Analytic plan for secondary objectives:

- PFS will be measured from the date of initiation of treatment to the first of documented progression or death; and will be estimated using the Kaplan-Meier method. PFS is expected to be comparable to that seen with 4/2 (11 month median); however if the upper bound of the interval is less than 8 months this will be taken as an indication that the efficacy of 2/1 is inferior to that of 4/2.
- Toxicities will be tabulated by type and grade, and the incidence of all  $\geq$  grade 3 toxicities will be calculated by CTCAE v 4.03 along with a 95% confidence interval
- The percentage of patients who underwent one or more dose reductions, dose interruptions and/or treatment delays will be estimated along with a 95% confidence interval. The number of patients who discontinue treatment due to unacceptable toxicities will be recorded, and reported as a percentage of the total number of enrolled patients along with 95% confidence interval.
- Health-related quality of life (HRQOL) will be assessed by FACT-G questionnaires as a secondary endpoint. Questionnaires will be administered at baseline, week 12, week 24 and week 36. Descriptive summary statistics will be calculated for all continuous variables (means, standard deviations, medians, ranges, percentage of patients scoring in the highest category for each item) for the items in the subscales each time point. The mean trajectories of each group over time will be plotted for the total scores, along with scores for physical well-being, emotional well-being, functional well-being, and renal-specific scales for FACT-G.

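### Table 3b forces a level reduction after a grade 2 LVEF decline or ventricular dysrhythmia, but permits a same-level restart when that type of event is grade 3 without heart failure

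*Combined protocol and SAP*

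**What the plan says.** All of this is in protocol section 7.0 unless another section is named.

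- **Grade 2 cardiac row.** Treatment continues at the same level, with two exceptions: an absolute LVEF fall of 20% to below the lower limit of normal, and a non-urgent paroxysmal ventricular dysrhythmia that needs intervention. For these the instruction is "withhold dose until toxicity is grade ≤1, then reduce the treatment by 1 level and resume treatment". A patient who was on level 0 must "resume at level -2", skipping level -1.
- **Grade 3 cardiac row.** There is no exception by event type: "Withhold dose until toxicity is grade ≤1 or has returned to baseline, then resume treatment at the same level", or one level lower if the investigator chooses.
- **Footnote to the grade 3 cardiac row.** It deals with blood pressure control and adds: "Patients with congestive heart failure must be removed from study".
- **Grade 4 cardiac row.** The patient leaves the protocol.
- **Floor of the ladder.** "If the current treatment level is -5 and the toxicity guidelines above indicate a further treatment/dose reduction is necessary, treatment should be discontinued".
- **Way back up.** "Intra-patient re-escalation back to the previous treatment level is permitted in the absence of grade" 3 or higher hematologic, or grade 2 or higher non-hematologic, treatment-related toxicity in the preceding cycle.
- **Time limit.** Toxicity that has not settled to grade 1 or less within 4 weeks off drug means removal. Section 6.3 has a similar stopping rule for grade 3 and 4 events. Neither rule sets a restart level.

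**The concern.** A dose-modification table should not require less as an event gets worse. For hematologic and for non-cardiac, non-hematologic toxicity, the required action in Table 3b rises with grade. For LVEF decline and ventricular dysrhythmia it is strict at grade 2, looser at grade 3, and then removal at grade 4.

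The special instruction to go from level 0 to level -2 indicates that the ordinary one-level step was thought insufficient for these events, since level -1 is still 50 mg. The grade 3 row nevertheless allows level 0 or level -1. Sections 1.3.6 and 8.1.1 associate more severe adverse events with higher drug exposure, so a looser dose rule after the worse event runs against the protocol's own reasoning.

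What is at stake is the safety of a few patients and consistency between sites. Two centers could handle the same grade 3 event differently and both comply.

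**Working it through.** The plan gives no figure to reproduce. The check is a reading of the rows side by side, followed by dose arithmetic.

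**Inputs.** Table 3a gives the dose and schedule of each level. Section 6.1 sets the cycle at 42 days. Section 16.3 plans 60 patients. Section 8.1.1 states that, at 50 mg, asymptomatic "decreases in cardiac ejection fraction were observed in <5% of solid tumor subjects".

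**Dosing days per full cycle.**
- 2 weeks on/1 week off: 14 of 21 days, so 28 of 42.
- 7 on/3 off/7 on/4 off: 7 + 3 + 7 + 4 = 21 days with 14 on, so again 28 of 42.

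Odd-numbered levels therefore change the pattern of dosing but not the cycle dose.

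**Cycle dose = 28 × daily dose.**
- Levels 0 and -1: 28 × 50 = 1,400 mg.
- Levels -2 and -3: 28 × 37.5 = 1,050 mg.
- Levels -4 and -5: 28 × 25 = 700 mg.

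**Least restrictive restart that each row allows.**

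| Level at event | Grade 2 listed event | Grade 3, no heart failure | Gap per full cycle |
|---|---|---|---|
| 0 | level -2, 1,050 mg | level 0, 1,400 mg | 350 mg |
| -1 | level -2, 1,050 mg | level -1, 1,400 mg | 350 mg |
| -2 | level -3, 1,050 mg | level -2, 1,050 mg | none; schedule only |
| -3 | level -4, 700 mg | level -3, 1,050 mg | 350 mg |
| -4 | level -5, 700 mg | level -4, 700 mg | none; schedule only |
| -5 | stop | level -5, 700 mg | stop versus 25 mg |

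From level 0, where every patient starts, the gap is (1,400 − 1,050)/1,400 = 25%. If the investigator takes the optional grade 3 step from level 0, the patient goes to level -1, which is still 1,400 mg.

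**Hold threshold.** The listed grade 2 events must settle to grade 1 or less. The grade 3 row also accepts a return to baseline.

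**Duration.** The event cycle itself contains a grade 2 or higher non-hematologic toxicity. If that toxicity is treatment-related, re-escalation has to wait for one clean 42-day cycle. The gap then lasts for what remains of the event cycle plus at least one more cycle. In the event cycle it is smaller than the full-cycle figure, because both rows require a hold and section 6.1 does not extend cycles for interruptions.

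**Number of patients.** Fewer than 0.05 × 60 = 3 with an asymptomatic ejection-fraction decrease. The share of these graded 3 without heart failure is an assumption, because the CTCAE cut-offs are not reproduced:

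| Assumed share | Patients |
|---|---|
| 0% | 0 |
| 10% | fewer than 0.3 |
| 50% | fewer than 1.5 |
| 100% | fewer than 3 |

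At 0% the point applies to ventricular dysrhythmia alone, for which the documents give no rate. The study calendar (section 3.2) lists no LVEF test.

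**The case against.** The strongest reply is that the dangerous cases are already covered. Heart failure and grade 4 cardiac events mean removal, and so does failure to settle within 4 weeks. The investigator may reduce under Table 3b or stop for safety under section 6.3. What remains is a resolved grade 3 event without heart failure, for which the investigator chooses the same level. Sections 1.3.6 and 8.1.1 describe LVEF declines as reversible, not cumulative, and possibly not recurring on reintroduction, so a same-level restart is medically defensible. This stands as a limit on the harm. It does not explain why discretion is withdrawn for the milder event and restored for the worse one, because those statements are not tied to a grade.

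It can also be said that the grade 3 counterpart of these events is an inference: the grade 2 dysrhythmia is specifically non-urgent, and the grading cut-offs are not in the documents. That is fair, and it is why the patient count is given as a range that includes zero for LVEF.

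The optional grade 3 reduction might be read as a step in milligrams instead of a step in level. It would still be optional.

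Three stronger readings are tempting, and the documents support none of them:

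- **A higher dose after the worse event at every level.** Not so. From levels -2 and -4 the forced grade 2 step changes only the schedule.
- **A shift in the discontinuation outcome through stops at level -5.** Section 16.5 says: "The number of patients who discontinue treatment due to unacceptable toxicities will be recorded". Section 6.3 defines an unacceptable event as grade 3 or 4 without recovery within 4 weeks. A stop at level -5 after a grade 2 event that has resolved does not clearly meet that definition.
- **A rule that is looser at grade 3 for all cardiac events, or that requires a same-level restart.** Other grade 2 cardiac events simply continue, so for them the table does rise with grade. The grade 3 row permits a same-level restart and does not require it.

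**Conclusion.** The point holds as a minor inconsistency in a safety rule. For LVEF decline and ventricular dysrhythmia, the mandatory minimum at restart is stricter at grade 2 than at grade 3 without heart failure, and no other text in the protocol closes the gap.

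From level 0 the difference is 37.5 mg against 50 mg. There is also a dose gap from levels -1 and -3, and at level -5 the contrast is stopping against continuing at 25 mg. The forced reduction can be reversed under the re-escalation rule, so the difference need not be permanent.

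The point rests on one assumption: that at least one of these event types can be graded 3 without heart failure. The number of patients is small and cannot be fixed from the documents. The primary endpoint (section 16.1) counts only fatigue, hand-foot syndrome and diarrhea, so neither it nor the sample size in section 16.3 is touched. No change in any study result is shown.

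**What to change.** Amend the grade 3 cardiac row of Table 3b so that LVEF decline and ventricular dysrhythmia without congestive heart failure receive at least the grade 2 action: hold to grade 1 or less, then a mandatory one-level reduction, going to level -2 if the patient was on level 0 and stopping if on level -5.

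Leave the rest as it is: removal for heart failure and for grade 4 cardiac events, the hypertension footnote, the re-escalation rule, and investigator discretion for other grade 3 cardiac events. If the asymmetry is intended, state the reason in section 7.0 instead.

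The cost is an amendment to one table row and a notice to sites, with no extra patients, visits or procedures. The downside is slightly less investigator discretion and a lower restart dose for a few patients.

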# Patient Pill Diary [Appendix 1] and instructed regarding its use to record each dose of oral medication.

# 6.2 General Concomitant Medications and Supportive Care Guidelines

Patients may receive Epogen/Procrit/Aranesp for anemia and a bisphosphonate for hypercalcemia and/or bone metastases as required. Anti-emetic therapy of any kind is permitted. Full transfusional support is permitted. The prophylactic use of growth factors is not allowed. The use of pyridoxine (vitamin B6) for the treatment of hand-foot syndrome is permitted. Palliative radiotherapy is allowed as long as there is no progressive disease per RECIST criteria; sunitinib may or may not be held during radiotherapy at the discretion of the treating physician. If held, dose changes must be recorded. No other approved or investigational anticancer treatment will be permitted during the study period, including chemotherapy, biological response modifiers, hormone therapy or immunotherapy. No other investigational drug may be used during treatment on this protocol, and concurrent participation in another clinical trial is not allowed.

Sunitinib is metabolized primarily by liver enzymes, in particular CYP3A4. Agents known to induce CYP3A4 including dexamethasone should be avoided. Agents known to inhibit this enzyme (e.g., grapefruit juice) should also be avoided. In particular, ketoconazole should be avoided if possible, since a clinical interaction study of sunitinib indicated that up to a 2-fold increase in plasma levels of sunitinib was induced by ketoconazole. In addition, concomitant treatment with the following drugs with dysrhythmic potential (ie, terfenadine, quinidine, procainamide, disopyramide, sotalol, probucol, bepridil, haloperidol, risperidone, and indapamide) is not recommended.

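### Table 3b orders a hold for grade 3 hematologic toxicity other than lymphopenia but tests only ANC and platelets for restart, so a hold for isolated grade 3 anemia has no effect

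*Combined protocol and SAP*

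**What the plan says.** **The row.** In Section 7.0, the Grade 3 Hematologic row of Table 3b reads "Withhold dose until ANC>1,000 and Platelets > 50,000, then resume treatment at the same level or reduce by 1 level at the discretion of the" (the discretion being the investigator's). It has no criterion for hemoglobin, for total white cells or for the grade of the event that led to the hold. Footnote \*\*\*, attached to this row and to the Grade 4 Hematologic row, adds: "Patients who develop grade 3 or 4 lymphopenia may continue study treatment without interruption". No other hematologic toxicity is exempted.

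**Neighbouring rows.** For grade 4 hematologic toxicity the text is "Withhold dose until toxicity is grade ≤1 or has returned to baseline, then reduce by 1 level and resume treatment". For grade 3 non-cardiac, non-hematologic toxicity, drug is held until the toxicity is grade 1 or less "or has returned to baseline, then resume treatment at the same level or reduce by 1 level at the discretion of the investigator". The grade 3 cardiac row has the same recovery condition.

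**Recovery rules.** After Table 3b: "Patients are to be removed from study if toxicity does not resolve to grade 1 or less within" 4 weeks off study drug. Section 6.3 ends treatment when a grade 3 or 4 toxicity "fails to recover to < Grade 2 in the absence of treatment within 4 weeks".

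**Supportive care.** Section 6.2 allows erythropoietic agents for anemia and states "Full transfusional support is permitted". Neither is linked to restarting sunitinib.

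**Endpoint.** Sections 16.2 and 16.5 report the percentage of patients with at least one dose reduction, interruption or delay, with a 95% confidence interval.

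**The concern.** A hold needs a release condition that looks at whatever caused the hold. This row's condition looks at two counts only. If the triggering toxicity lies elsewhere and both counts are adequate, the instructions to withhold and to resume apply on the same day with the toxicity unchanged.

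Two things are at stake. The first is safety: read literally, the row lets dosing continue, at the same level if the investigator chooses, through an unresolved grade 3 toxicity that the same row says to hold for. The second is the dose-interruption endpoint, since the same blood counts give either no interruption or a counted one, depending on whether the restart test is applied as written or the toxicity is expected to recover first.

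**Working it through.** The plan gives no figure to reproduce here. The check applies the row as a logical rule, reads it against the other rules, and then bounds the size.

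**Step 1. The rule as written.** Release if ANC > 1,000 and platelets > 50,000. The counts below are illustrative assumptions, not figures from the documents.

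| Triggering event | ANC | Platelets | Result |
|---|---|---|---|
| Grade 3 anemia alone | 3,000 | 200,000 | released at once |
| Grade 3 leukopenia | 1,200 | 150,000 | released at once |
| Grade 3 leukopenia | 900 | 150,000 | held |
| Neutropenia | 800 | 150,000 | held |
| Thrombocytopenia | 3,000 | 40,000 | held |
| Grade 3 lymphopenia | any | any | no hold required (footnote) |

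The rule works for neutropenia and thrombocytopenia. It fails for isolated anemia, and for leukopenia only when both counts already pass.

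**Step 2. Do the 4-week rules close the gap?** Section 6.3 measures recovery in the absence of treatment. The removal rule after Table 3b measures it over 4 weeks off study drug. A patient released at once accrues no time off drug from the hold. The planned break on schedule 2/1 is one week, short of four. Neither rule is reached, and neither states a restart condition.

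**Step 3. Comparison within the table.** The grade 3 cardiac, grade 3 non-cardiac/non-hematologic and grade 4 hematologic rows all require the toxicity itself to reach grade 1 or less, or baseline. Among the rows that order a hold for grade 3 or 4 toxicity, only the Grade 3 Hematologic row does not. Section 7.0 also makes re-escalation depend on there having been no grade 3 or higher treatment-related hematologic toxicity in the previous cycle. Treatment-related grade 3 anemia therefore counts for that rule, although it has no working hold.

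**Step 4. Size.** Inputs are n = 60 (Section 16.3) and an assumed grade 3 anemia rate of 3-8%, because the documents give none.

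- Patients affected: 0.03 × 60 = 1.8 and 0.08 × 60 = 4.8, so about 2-5.
- Each patient is 100/60 = 1.7 percentage points.
- Largest shift in the interruption percentage: 1.8/60 = 3 points to 4.8/60 = 8 points. This needs every affected patient to have no other qualifying event.
- Allowing for overlap: Section 1.2 reports interruptions in 38% of patients in the phase III trial on schedule 4/2. If that rate applied here, independently of anemia, the shift would be (1 − 0.38) × 3 = 1.9 to (1 − 0.38) × 8 = 5.0 points. It would be smaller again once reductions and delays are counted.

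**The case against.** The strongest defence is that the row was written for neutropenia and thrombocytopenia and is merely loosely labelled. Section 8.1.1 names those two as the main hematologic events. Anemia is dealt with through supportive care in Section 6.2, and Section 4.1 permits transfusion to meet the hemoglobin criterion. This is plausible, but the documents do not say it. The row is headed for hematologic toxicity in general, and the only exemption is lymphopenia. What stands is that the authors' intent cannot be settled from the text.

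For that reason, a reader might infer from the lymphopenia exemption that anemia and leukopenia were meant to be held until recovery. That does not follow. The same footnote sits on the grade 4 row, where restart requires recovery, so the exemption has a function there whatever was intended for grade 3 anemia.

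Investigator discretion also limits the harm. The row permits resumption at the same level but does not compel it, and Section 6.3 lets the investigator stop treatment for safety. That discretion covers the level on resumption and permanent discontinuation. It does not supply the missing release condition.

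A reader might also expect sites to diverge in practice. The documents give no evidence that they do; they show only that the text allows two readings.

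Finally, the endpoint concerned is descriptive with no decision threshold, and the leukopenia case is narrow. Both points stand and keep the matter modest.

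**Conclusion.** The point holds as a defect in a stated rule. Followed literally, the Grade 3 Hematologic row orders a hold that has no effect in isolated grade 3 anemia, and in grade 3 leukopenia when ANC and platelets already exceed the thresholds. The 4-week rules do not repair it.

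It does not extend to every grade 3 hematologic toxicity: lymphopenia is exempt, and the test works for neutropenia and thrombocytopenia.

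The estimate of about 2-5 of 60 patients rests wholly on the assumed 3-8% anemia rate. The 3-8 point shift is an upper limit under that assumption and should not be read as the expected effect. The primary endpoint is not affected, since its components are fatigue, hand-foot syndrome and diarrhea. The reasons to act are patient safety, an unambiguous interruption endpoint and the low cost.

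**What to change.** The sponsor should reconcile four places: the Grade 3 Hematologic row of Table 3b, footnote \*\*\*, the removal rule after Table 3b, and Section 6.3. Together they should state consistently how grade 3 hematologic toxicities other than neutropenia and thrombocytopenia are handled. Which rule applies is the sponsor's clinical decision, and none is proposed here. Sections 16.2 and 16.5 should then count dose interruptions by the same rule.

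The same edit can settle a related mismatch: the row releases drug on ANC and platelet thresholds, while the removal rule asks for resolution to grade 1 or less.

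The cost is about one line in Table 3b or its footnote, plus matching wording in the endpoint definition. The scheduled CBC in the study calendar already covers the blood counts, so no new assessment is needed.

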#### 3.0 STUDY DESIGN

# 3.1 Study schema

This is a single arm phase II study of sunitinib administered to treatment-naïve patients with clear cell mRCC. Patients will be treated with sunitinib at a starting dose of 50mg 2/1 with schedule/dose modifications for toxicity and treated until RECIST-defined progressive disease or unacceptable toxicity. Adverse events will be graded and categorized using CTCAE version 4.03 criteria. Staging studies will be assessed per RECIST v 1.

Sunitinib starting dose 50 mg by mouth daily given for 2 weeks "on" followed by 1 week "off" 1 cycle=6 weeks

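### Table 3b requires a hold for every vascular toxicity, yet its grade 2 row says to continue, and its hypertension footnote also allows continuation if hypertension counts as vascular

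*Combined protocol and SAP*

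**What the plan says.** All of the relevant text is in Section 7.0, Table 3b and its footnotes, unless noted.

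- **Grade 1 row.** It leaves the treatment level unchanged and is labelled "Any except vascular", with a pointer to the `+` footnote. It is the only row that carries the exception.
- **Footnote `+`.** It says that "for all vascular toxicities, including grade 1, drug must be held and appropriate treatment initiated", and then "Sunitinib may be restarted at the discretion of the treating MD".
- **Grade 2, non-cardiac and non-hematologic row.** "Continue at same dose level".
- **Grade 3, same category.** Hold until the event is at grade 1 or lower "or has returned to baseline, then resume treatment at the same level or reduce by 1 level at the discretion of the investigator".
- **Grade 4, same category.** Hold to the same recovery point, "then reduce by 1 level and resume treatment, or discontinue at the discretion of the investigator".
- **Footnote `**`.** "Hypertension may be managed appropriately with anti-hypertensives, and the patient may continue sunitinib provided the blood pressure is controlled" to below 160/90 mmHg within 4 weeks. If control is not reached in that time, the patient leaves the study.

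The table has no vascular row for grades 2 to 4, and the protocol does not define vascular. Section 3.1 says "Adverse events will be graded and categorized using CTCAE version 4.03 criteria", but the documents do not reproduce the category list.

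**The concern.** A grade 2 vascular event is neither cardiac nor hematologic, so it falls in a row that tells the site to continue. The footnote tells the same site to hold. The exception is written on the grade 1 row and not on the grade 2 row, so a site can reasonably conclude that the grade 2 row applies as printed.

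Hypertension raises a second version of the same question. If it is vascular, one footnote requires a hold and the other permits continuation. Neither refers to the other.

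These events are foreseeable. Section 1.3.6 lists hypertension among the most common related events of grade 3 maximum severity (5.8%) and pulmonary embolism among the most serious related events (1.1%). Section 4.1 admits patients with prior thromboembolism who are on anticoagulation. The trial is multicenter (Section 14.0), so sites may act differently on the same event. The main stake is patient safety. The secondary stake is the percentage of patients with any dose reduction, interruption or delay (Sections 16.2 and 16.5), because an event that is held counts there and an event that is continued need not.

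**Working it through.** **Step 1. Compare the instructions by grade for a vascular event.**

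| Grade | Row | Footnote `+` | Compatible? |
|---|---|---|---|
| 1 | No change, vascular excepted | Hold | Yes, because of the stated exception |
| 2 | Continue, no exception | Hold | No |
| 3 | Hold to grade 1 or lower, or baseline; then same level or one lower | Hold; restart at discretion | Yes |
| 4 | Hold to the same point; then one level lower, or stop | Hold; restart at discretion | Yes |

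At grades 3 and 4 the footnote permits a restart but does not compel one. A physician can hold, wait for the row's recovery point, apply the row's level rule and then restart, and so comply with both.

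Two further rules limit an open-ended restart. The text after Table 3b removes patients whose toxicity has not resolved to grade 1 or lower within 4 weeks off drug. Section 6.3 ends treatment for a grade 3 or 4 toxicity that has not recovered to below grade 2 within 4 weeks off treatment.

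**Step 2. Compare the two footnotes for hypertension.** If hypertension is vascular, `+` requires a hold and `**` permits continuation. If it is not vascular, `+` does not apply and there is no conflict. The documents do not settle which holds.

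**Step 3. Size the effect on the secondary composite.** The plan gives no figure of its own to reproduce. The inputs are:

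- n = 60 (Section 16.3)
- hypertension prevalence h = 10% before and 5% after schedule change (Section 1.4, Table 2; grade not stated)
- phase III interruption rate 38% and reduction rate 32% (Section 1.2)

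Effect of one patient: 1/60 = 1.7 points.

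Patients with hypertension: 60 × 0.05 = 3 and 60 × 0.10 = 6.

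Share already counted in the composite, u, from interruptions and reductions with delays ignored:

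- lowest, if one group lies wholly inside the other: max(38%, 32%) = 38%
- highest, if the groups do not overlap: 38% + 32% = 70%

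Net shift = h × (1 − u), assuming that hypertension is independent of being already counted:

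| h | u = 70% | u = 38% |
|---|---|---|
| 5% | 0.05 × 0.30 = 1.5 points | 0.05 × 0.62 = 3.1 points |
| 10% | 0.10 × 0.30 = 3.0 points | 0.10 × 0.62 = 6.2 points |

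For scale, the 95% half-width with 60 patients is 1.96 × √(0.38 × 0.62/60) = 12.3 points at 38%, and 1.96 × √(0.70 × 0.30/60) = 11.6 points at 70%.

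This covers the hypertension conflict only. The documents give no rate for other grade 2 vascular events, so that conflict is not sized.

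**The case against.** The strongest reply is that the `+` footnote speaks of all vascular toxicities and names grade 1 only as an inclusion. It therefore governs every grade, and a specific rule displaces the general row. By the same logic `**`, which names a single event, is narrower than `+` and prevails for hypertension. The `**` marker also appears on the grade 3 cardiac row, and its text deals with congestive heart failure as well. The authors may therefore have treated hypertension as cardiac, in which case `+` never reaches it.

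This is a reasonable account of what was intended, but the protocol states no order of precedence, and marking the exception on one row only invites the opposite reading. The cardiac reading also raises a new question, because the grade 4 cardiac row removes the patient from protocol. Depending on an undefined label, grade 4 hypertension could mean hold, continue or remove.

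It is also fair to object that the table is broken near the grade 2 row in the machine-read text. Marker placement should be checked in the original PDF. The conflict between the footnotes rests on their sentences and not on the markers.

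A reader might infer that grades 3 and 4 conflict as well, since `+` names no recovery threshold and no reduction. The documents do not support that: Step 1 shows that both instructions can be followed, within the 4-week removal rules.

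**Conclusion.** One opposition stands outright: hold under `+` against continue in the grade 2 non-cardiac, non-hematologic row. A second stands on the condition that hypertension is vascular: hold under `+` against permission to continue under `**`. Both matter mainly for patient safety and for consistency between sites.

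The statistical effect is small. Each patient handled differently moves the secondary composite by 1.7 points, and the hypertension conflict might move it by roughly 1.5 to 6.2 points, against a half-width of about 12. That range is illustrative. It borrows rates from other cohorts, ignores delays, and assumes that every patient with hypertension would be held under one footnote and continued under the other. Section 16.5 attaches no decision rule to this endpoint.

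A reader might infer that the trial's main result is at risk. It is not: the primary endpoint counts fatigue, hand-foot syndrome and diarrhea only (Section 16.1), and the hold rules for vascular events do not enter its definition.

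**What to change.** Amend Table 3b as follows.

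1. Label the grade 2 non-cardiac and non-hematologic row as excepting vascular events, with the `+` marker.
2. Add to footnote `+`: *Hypertension is managed under the double-asterisk footnote, not under this footnote. For grade 3-4 vascular toxicity the recovery and level-reduction conditions in the rows above still apply before restart.*
3. Have the sponsor state whether grade 4 hypertension requires a hold, and write the answer into footnote `**`.

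Footnote `+` should not be made to override the grade 3 and 4 rows. That would drop the recovery threshold and the grade 4 requirement to reduce or discontinue. Check marker placement in the original PDF before editing.

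The cost is one row label, two sentences in a footnote and one clinical decision by the sponsor. No visits, procedures or patients are added.
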